##### **4.2.4.2 Study treatment compliance**

Study treatment compliance will be summarized by treatment group for the FAS and calculated as:

$$\text{Study treatment compliance} = (\text{total doses administered} / \text{total doses expected}) \times 100.$$

Patients who received no study treatment will have zero compliance. Total number of doses expected includes all visits with protocol scheduled IP administration on or before a subject's IP discontinuation or treatment complete date.

#### **4.2.5 Primary outcome variable**

##### **4.2.5.1 Primary analysis**

The change from baseline in pre-BD FEV1 up until the EOT at Visit 10 will be compared between the 30 mg benralizumab group and placebo using a mixed-effect model for repeated measures (MMRM) analysis on patients with a baseline pre-BD FEV1 and at least 1 post-randomization pre-BD FEV1 in the FAS.

The dependent variable will be the change from baseline in pre-BD FEV1 at post-baseline protocol specific visits (up to and including the EOT Visit). Treatment group will be fitted as the explanatory variable, region, visit and treatment\*visit interaction as fixed effects, and baseline pre-BD FEV1 will be fitted as a covariate. The variance-covariance matrix will be assumed to be unstructured. If the procedure does not converge, then a compound symmetric variance-covariance matrix will be used instead. The model is:

$$\text{Change in FEV}_1 = \text{treatment} + \text{baseline pre-BD FEV}_1 + \text{region} + \text{visit} + \text{treatment} * \text{visit}$$

The primary objective of the study is to determine the effect of benralizumab on the time course of change (onset and maintenance of effect) of pre-BD FEV1 using the model described above. The first post-baseline timepoint where the p-value for the mean difference between benralizumab and placebo is  $\leq 0.05$  will be used to determine time to onset of effect. The average over the mean differences between benralizumab and placebo based on the change from baseline (Visit 4) to Days 28 (Visit 8), 56 (Visit 9), and 84 (Visit 10) in pre-BD FEV1 will be used to determine if the study is positive as well as to determine the

maintenance of effect. Contrasts will be used to obtain estimates of the treatment differences over Days 28, 56, and 84, as well as at each timepoint separately.

Results will be presented in terms of least square means (LSMEANS), treatment differences in LSMEANS, 95% confidence intervals (CI) of treatment differences, and p-values at each planned timepoint.

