3.1.1 Additional inclusion criteria applicable for the Body Plethysmography sub-study

1. Residual volume $\geq 125\%$ of predicted at Visit 3.

Patients who do not meet this criterion and/or are not able to take body plethysmography assessments, should continue in the main study only.

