3.6 Methods for assigning treatment groups

Patients will be stratified by geographical region and also by whether patients enter the whole body plethysmography sub-study. Randomization codes will be assigned strictly sequentially in each stratum as patients become eligible for randomization.

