5.3.8.2 Chain of custody of biological samples

A full chain of custody is maintained for all samples throughout their lifecycle.

The Principal Investigator at each center keeps full traceability of collected biological samples from the subjects while in storage at the center until shipment or disposal (where appropriate) and keeps documentation of receipt of arrival (where applicable).

The sample receiver keeps full traceability of the samples while in storage and during use until used or disposed of or until further shipment and keeps documentation of receipt of arrival.

AstraZeneca keeps oversight of the entire life cycle through internal procedures, monitoring of study sites and auditing of external laboratory providers.

Samples retained for further use are registered in the AstraZeneca biobank system during the entire life cycle.

5.4 Additional assessments applicable for the subset of subjects – body plethysmography sub-study

Additional assessments will be performed for a subset of subjects at designated sites, approximately 50 subjects in the study, to determine the effect of benralizumab on the time course of change in lung function as assessed through body plethysmography.

Patients who participate in the sub-study will perform other lung function assessments as mentioned in sections 4.1.1, 4.1.2, 4.1.3, 4.2 and 4.3.

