8.5.1 Analysis of the primary variable(s)

The change from baseline in pre-BD FEV₁ up until the EOT at Visit 10 will be compared between the 30 mg benralizumab group and placebo using a repeated measures analysis on patients with a baseline pre-BD FEV₁ and at least 1 post-randomization pre-BD FEV₁ in the full analysis set. The dependent variable will be the change from baseline in pre-BD FEV₁ at post-baseline protocol specific visits (up to and including the EOT Visit). Treatment group will be fitted as the explanatory variable, region, visit and treatment*visit interaction as fixed

effects and baseline pre-bronchodilator FEV₁ as a covariate. The variance-covariance matrix will be assumed to be unstructured. If the procedure does not converge then a compound symmetric variance-covariance matrix will be used instead. The model is:

$$\text{Change in FEV}_1 = \text{Treatment group} + \text{baseline pre-BD FEV}_1 + \text{region} + \text{visit} + \text{treatment} * \text{visit}$$

The primary objective of the study is to determine the effect of Benralizumab on the time course of change (onset and maintenance of effect) of pre-BD FEV₁ using the model described above. The first post baseline timepoint where the p-value for the mean difference between benralizumab and placebo is less than or equal to 0.05 will be used to determine time to onset of effect. The average over the mean differences between benralizumab and placebo based on the change from baseline (Visit 4) to Days 28 (Visit 8), 56 (Visit 9) and 84 (Visit 10) in pre-BD FEV₁ will be used to determine if the study is positive as well as maintenance of effect. Contrasts will be used to obtain estimates of the treatment differences over Days 28, 56 and 84 as well as at each timepoint separately.

Additional supportive analyses to the primary objective of the study will be carried out as detailed below.

The modelled treatment response as well as differences between benralizumab and placebo using the mean change from baseline in pre-BD FEV₁ endpoint using an exponential model over time will be estimated. The model will be used to determine the modelled time to onset of effect where the pre-BD FEV₁ reaches thresholds for improvement in both mean differences between benralizumab and placebo as well as within treatment change from baseline differences. If the exponential model does not fit the time profile alternative models will be assessed.

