## 1.3 Number of subjects

The study will recruit approximately 230 patients in total and 115 patients in each treatment group based on the primary objective of the study to determine the effect of benralizumab on the time course of change (onset and maintenance of effect) of pre-bronchodilator (BD) FEV1.

Patients will be randomized in a 1:1 ratio to benralizumab or placebo. In order to have a balanced number of patients for each region and the body plethysmography sub-study, the randomization will be stratified by these variables.

The study is powered for the primary objective of the study to determine the effect of benralizumab on the time course of change (onset and maintenance of effect) of pre-BD FEV1.

The first post-baseline timepoint where the p-value for the mean difference between benralizumab and placebo is  $\leq 0.05$  will be used to determine time to onset of effect. The average over the mean differences between benralizumab and placebo based on the change from baseline (Visit 4) to Days 28 (Visit 8), 56 (Visit 9), and 84 (Visit 10) in pre-BD FEV1 will be used to determine if the study is positive and to determine maintenance of effect.

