## **4.2.6 Secondary efficacy outcome variables**

### **4.2.6.1 Secondary analyses**

For each secondary efficacy variable described in Section 3.2, the objective is to determine the effect of benralizumab on the time course of change (onset and maintenance of effect).

FEV1 responder at each post-baseline visit will be defined as a subject with change from baseline  $\geq$  prespecified cutoffs as in Section 3.1, and analysed using a logistic regression model with repeated measures using generalized equation estimate method. The model will include treatment, region, visit and treatment group by visit interaction as fixed factors, and baseline FEV1 scores as a covariate. The variance-covariance matrix will be assumed to be unstructured.

The percent change from baseline at each timepoint for the eosinophils counts, change from baseline at each timepoint for Pre-BD FVC, ACQ-6 score, SGRQ score, and FeNO will be compared between benralizumab and placebo using an MMRM analysis described in the primary analysis above. The least squares mean for the difference in treatment groups using the interaction between visit and treatment group, its 95% CI, and the 2-sided p-values will be reported for each post-baseline visit.

As for the primary endpoint, the first post-baseline timepoint where the p-value for the mean difference between benralizumab and placebo is less than or equal to 0.05 from the repeated measures analysis will be used to determine time to onset of effect for each secondary parameter. The average over the mean differences between benralizumab and placebo based on the change from baseline (Visit 4) to Days 28 (Visit 8), 56 (Visit 9), and 84 (Visit 10) will be used to determine maintenance of effect. Contrasts will be used to obtain estimates of the average treatment differences over Days 28, 56, and 84.

Results will be presented in terms of LSMEANS, treatment differences in LSMEANS, 95% CIs of treatment differences, and p-values at each planned timepoint. To explore correlations between changes in eosinophil depletion and lung function, and correlations between changes in FeNO and lung function, the following analyses will be conducted, blood eosinophil data collected at Screening visit will be used in the analyses below to be consistent with the subgroup analysis of pre-BD FEV1 by baseline EOS categories:

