The assumptions that will be used to impute the missing data who withdraw early are as follows:

- (a) MAR: Assumes that the trajectory for patients who dropped out in each arm is similar to those observed in their own treatment arm
- (b) DRMI: Assumes that the trajectory for patients in the benralizumab arms who dropped out for a treatment related reasons (according to the classification for DRMI) is similar to that of the placebo patients, whereas the remaining patients who has dropped out are imputed assuming MAR.

Approach b) can be considered more conservative than the approach for the primary analysis because the assumptions mean that as soon as patients withdraw for a treatment related reason, they begin to worsen immediately.

The MNAR imputation is achieved by using only appropriate data at each stage of the imputation. Imputation will be done in 2 steps, the non-monotone (intermediate) missing FEV1 values will be imputed first (Markov chain Monte Carlo [MCMC] method is used to partially impute the data using SAS PROC MI) and then the missing value at each visit will be imputed using a sequential regression method (using MONOTONE REG option of SAS PROC MI).

For example, to impute missing values at time  $t$  for patients in the benralizumab arms who dropped out due to an AE, include only placebo observations up to and including time  $t$ , plus observations from patients in the benralizumab arms, that dropped out due to an AE, up to and including time  $t-1$ . This is carried out for each visit, 1 at a time using observed data, and missing values imputed up until that visit. Placebo missing observations and benralizumab observations that are not missing due to AEs are imputed assuming missing at random (MAR) and follow the pattern of observed placebo observations in each treatment arm, respectively. One-hundred imputations will be carried out. A seed of 784088 will be used for the monotone imputation step and a seed of 409345 will be used for the sequential regression imputation step. The analysis of each imputed dataset will be as described for the primary analysis in Section 4.2.5.1 and these will be combined using SAS procedure PROC MIANALYZE.

To avoid possible convergence issues when fitting MMRM models to 100 imputed datasets, the estimated unstructured covariance parameters from the first imputation where the model converges will be used as the starting values to fit the models for all imputed datasets.

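### Randomization is stratified by region and plethysmography sub-study participation, but the primary and secondary MMRMs adjust only for region, so the SE is slightly too large if sub-study status is prognostic

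*SAP*

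**What the plan says.** Protocol 3.6 names two stratification factors: "Patients will be stratified by geographical region and also by whether patients enter the whole body plethysmography sub-study". SAP 1.3 repeats them and gives the purpose, a "balanced number of patients for each region and the body plethysmography sub-study, the randomization will be stratified by these variables".

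The primary model carries one of the two. Protocol 8.5.1 states "Treatment group will be fitted as the explanatory variable, region, visit and treatment*visit interaction as fixed" effects, with baseline pre-bronchodilator FEV1 as a covariate. SAP 4.2.5.1 gives the same model: "Treatment group will be fitted as the explanatory variable, region, visit and treatment"-by-visit interaction, plus the baseline covariate. The model equation printed in each document has no sub-study term.

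The same model is used again elsewhere. In SAP 4.2.6.1 the secondary endpoints "will be compared between benralizumab and placebo using an MMRM analysis described in the primary analysis above". In SAP Appendix 8.1, "The analysis of each imputed dataset will be as described for the primary analysis in Section 4.2.5.1".

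No other section adds the factor or explains its absence. SAP section 6 (changes from protocol) covers only ECG. The sensitivity analysis in SAP 4.2.5.2 concerns withheld medication, and the subgroup list in SAP 4.2.5.3 names region but not sub-study status. The sub-study's own models (SAP 4.2.8) need no such term, because every patient in them belongs to that stratum.

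**The concern.** Stratified randomization balances the stratum between the arms. If the stratum predicts outcome, its between-stratum variance no longer contributes to the true variability of the treatment difference. A model without the stratum term still counts that variance as residual. The reported SE then exceeds the true SE, confidence intervals are too wide and the test is conservative. This applies to the Day 28/56/84 average that decides whether the study is positive, and to the single-visit p-values that define onset at the 0.05 threshold.

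It is plausible, though not shown in the documents, that sub-study status is prognostic. Entry requires a residual volume of at least 125% of predicted at Visit 3 (Protocol 3.1.1). It happens only at selected centers: "Additional assessments will be performed for a subset of subjects at designated sites, approximately 50 subjects in the study" (Protocol 5.4). Sub-study patients must also show reversibility by Visit 2, while other patients have until Visit 3 (Protocol 3.1, criterion 7).

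The contrast is diluted, however. Protocol 3.1.1 says: "Patients who do not meet this criterion and/or are not able to take body plethysmography assessments, should continue in the main study only". Centers outside the sub-study do not measure residual volume at all, so the other stratum also contains patients with high values. Baseline FEV1 and region, already in the model, may absorb part of any difference.

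**Working it through.** **Inputs.** From SAP 1.3: 115 patients per arm, 1:1 allocation, two-sided alpha 0.05, within-group SD 375 mL, within-patient correlation 0.6, and a true average difference of 138 mL over three visits. From Protocol 5.4: about 50 of the 230 patients in the sub-study. The difference *d* in mean FEV1 change between strata, remaining after baseline FEV1 and region, is **assumed**; a range of 25 to 200 mL is shown.

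**The plan's own figure.** The variance of the three-visit average is V = 375² × (1 + 2 × 0.6)/3 = 103,125 mL², an SD of 321.1 mL. The SE of the treatment difference is √(2 × 103,125/115) = 42.35 mL. Power at 138 mL is Φ(138/42.35 − 1.96) = 90.3%, which reproduces the stated 90%.

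**Effect of the omitted term.** With p = 50/230, p(1 − p) = 0.1701.

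- Between-stratum variance: B = 0.1701 × d²
- Reported SE without the term: √(2V/115)
- True SE, and the SE with the term: √(2(V − B)/115)
- Actual type I error without the term: 2 × [1 − Φ(1.96 × reported SE/true SE)]

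Three-visit average, reported SE 42.35 mL throughout:

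| d (mL) | B (mL²) | True SE (mL) | SE excess | Actual type I error |
|---|---|---|---|---|
| 25 | 106 | 42.33 | 0.05% | 4.99% |
| 50 | 425 | 42.26 | 0.2% | 4.95% |
| 100 | 1,701 | 42.00 | 0.8% | 4.8% |
| 150 | 3,828 | 41.56 | 1.9% | 4.6% |
| 200 | 6,805 | 40.93 | 3.5% | 4.3% |

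**Power at 138 mL.** Without the term it is Φ((138 − 1.96 × 42.35)/true SE). With the term it is Φ(138/true SE − 1.96).

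- d = 100 mL: 90.5% without, 90.8% with
- d = 200 mL: 91.1% without, 92.1% with

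**Single-visit onset test.** V = 375² = 140,625 mL², so the reported SE is 49.45 mL.

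- d = 100 mL: true SE 49.15 mL, excess 0.6%, type I error 4.9%
- d = 200 mL: true SE 48.24 mL, excess 2.5%, type I error 4.45%

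**Simulation check.** The three-visit average was simulated with allocation fixed at 25/25 in the sub-study and 90/90 outside it, and analysed by a linear model with and without the stratum term. Null rejection rates were:

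| Run | d (mL) | Without term | With term |
|---|---|---|---|
| 40,000 trials | 100 | 4.8% | 5.0% |
| 40,000 trials | 200 | 4.35% | 5.1% |
| 20,000 trials | 100 | 5.07% | 5.27% |
| 20,000 trials | 200 | 3.98% | 4.74% |

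The simulation standard error at 20,000 trials is √(0.05 × 0.95/20,000), about 0.15 percentage points. The smaller run therefore cannot separate the 100 mL case from 5%. In every row the rate is lower without the term. In the smaller run at 200 mL, the mean reported SE without the term was 42.3 mL against an empirical SD of 40.6 to 41.1 mL; with the term it was 40.9 mL.

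**The case against.** The omission and the arithmetic are not disputed. The case on the other side concerns consequence.

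- **No harm is demonstrated.** The estimate is unbiased, type I error is not inflated and power holds. The loss exists only if sub-study status is prognostic, which the documents do not show. This stands, and it is why the point is minor and conditional.
- **The realistic effect is negligible.** At 50 mL the 95% confidence interval half-width changes by 1.96 × (42.35 − 42.26), under 0.2 mL; at 100 mL by about 0.7 mL. A 200 mL residual difference would exceed the 138 mL treatment effect and would have to survive adjustment for baseline FEV1 and region. This also stands.
- **The figures are close to an upper bound for each d.** They assume exact balance within the sub-study strata. The protocol gives no block size, and patients without usable FEV1 data drop out of the analysis. Imbalance would move the true SE towards the reported one. This is correct.
- **Stratification was meant to balance numbers, not to reflect prognosis.** SAP 1.3 supports that reading. It explains why the factor is in the randomization, but not why the analysis ignores it while keeping region, which was stratified for the same stated purpose.
- **Secondary p-values are nominal (SAP 4.1), and the onset rule scans six visits without multiplicity adjustment.** True, so slight conservatism there changes no controlled decision. The estimates and intervals are still reported from these models.
- **Adding the term only to the analysis of imputed data could leave it out of step with the imputation model, and the responder models share the omission.** This is a fair addition to the remedy, not a reason against it.

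**Conclusion.** The concern holds and is minor. The omission is certain from the text of both documents. Its direction is conservative: the SE is too large or, if sub-study status is not prognostic, correct.

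The size is uncertain because it rests on an assumed stratum difference. The lower part of the range is the more realistic, roughly a 0.05% to 0.8% SE excess for 25 to 100 mL. Even at 200 mL the power gained is only about one percentage point. A slightly inflated SE could change a conclusion only for a result close to the 0.05 threshold, such as a borderline visit in the onset rule.

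The calculation further assumes the plan's SD and correlation, a sub-study of 50 patients, exact balance within strata, and a stratum difference that acts as a constant shift across visits. The effect on the secondary endpoints was not computed.

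**What to change.** Add sub-study participation (yes/no, as randomized) as a fixed effect to the primary MMRM in SAP 4.2.5.1, to the secondary MMRMs in SAP 4.2.6.1 that reuse it, and to the model applied to each imputed dataset in SAP Appendix 8.1. For consistency, include the factor in the imputation regressions, and consider it for the responder GEE and logistic models, which also carry region alone. Record the change against Protocol 8.5.1 in SAP section 6.

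The cost is SAP wording and one degree of freedom per MMRM. The variable is already held in the randomization system, so no new data are needed. If the sponsor keeps the present model, the SAP should say why one stratification factor is fitted and the other is not. That is the weaker option, since it leaves the possible excess in the SE in place.

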- 20. Receipt of any marketed (eg, omalizumab, mepolizumab etc.) or investigational biologic within 4 months or 5 half-lives prior to the date informed consent is obtained, whichever is longer
- 21. Receipt of live attenuated vaccines 30 days prior to the date of randomization.
- 22. Receipt of any investigational medication within 30 days or 5 half-lives prior to randomization, whichever is longer
- 23. Previously received benralizumab (MEDI-563)
- 24. Planned surgical procedures during the conduct of the study
- 25. Currently breastfeeding or lactating women
- 26. Previous randomization in the present study
- 27. Concurrent enrolment in another interventional or post-authorization safety study (PASS).
- 28. AstraZeneca staff involved in the planning and/or conduct of the study
- 29. Employees of the study center or any other individuals involved with the conduct of the study or immediate family members of such individuals

3.3 Eligibility criteria to be confirmed at randomization Visit 4.

3.3.1 Inclusion criteria at randomization Visit 4

1. At least 1 of the following within 7 days prior to randomization:
 - Daytime or nighttime asthma symptoms for 2 or more days;

- Rescue SABA use for 2 or more days;
 - Nighttime awakenings due to asthma at least 1 night during the 7-day period
2. ACQ >0.75 at Visit 4 prior to randomization.
 3. A negative urine pregnancy test in WOCBP prior to administration of IP

3.3.2 Exclusion criteria at randomization Visit 4

1. Greater than/equal to 20% change in mean Pre BD FEV1 value (mean of the Pre BD FEV1 taken 30 min (+/- 10 min) and 60 min (+/- 10 min) prior to dosing) at randomization Visit 4 (Day 0) from the mean pre BD FEV1 calculated from the pre BD FEV1 recorded at Visit 2 and Visit 3.

Procedures for withdrawal of incorrectly enrolled subjects see Section 3.5.

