4. STUDY PLAN AND TIMING OF PROCEDURES

Table 2 Study plan - Run-in period; Visit 1 to Visit 3

Assessment/Activity	Refer to	Enrolment	Run-in	
		Visit 1	Visit 2	Visit 3
		D -35	D -21 (+/-2 days)	D -7 (+/- 2 days)
General procedures:				
Informed consent	10.4	X		
Inclusion/exclusion criteria	3.1/3.2	X	X	X
Demographics	4.1.1	X		
Medical and asthma history	4.1.1	X		
Patient Reported Outcome assessments:				
ACQ-6	5.3.2.1	X ^c		
Safety assessments:				
Complete physical examination	5.2.2.1/5.2.2.2	X		
Vital signs	5.2.4		X	X
Weight, height, BMI	5.3.1	X		
ECG	5.2.3.1	X		
Adverse events	6	X	X	X
Concomitant medication	7.7/3.9.1/3.9.1.1	X	X	X
Laboratory assessments:				
Clinical chemistry	5.2.1	X		
Hematology	5.2.1	X		
Urinalysis	5.2.1	X		
Serum pregnancy test	5.2.1.1	X		
Serology (Hepatitis B, C, HIV-1, HIV-2)	5.3.3.1	X		
FSH	5.2.1.1	X ^b		
Lung function assessments:				

Table 2 Study plan - Run-in period; Visit 1 to Visit 3

Assessment/Activity	Refer to	Enrolment	Run-in	
		Visit 1	Visit 2	Visit 3
		D -35	D -21 (+/-2 days)	D -7 (+/- 2 days)
Exhaled NO (FeNO)	5.1.2		X	
Spirometry (Pre-BD FEV ₁)	5.1.1		X ^d	X ^d
Reversibility (post-BD FEV ₁)	5.1.1.1	X ^{e,f}	X ^{e,f}	X ^e
Sub-study assessments (if applicable):				
Whole body plethysmography	5.4.1			X

- a This analysis will be only applicable for WOCBP patients.
- b FSH test done only for female patients to confirm postmenopausal status in women <50 years who have been amenorrheic for >=12 months
- c All patients must meet ACQ6 ≥1.5 at Visit 1. If this criteria is not met the patient must be screen failed and will not be allowed to rescreen.
- d For patients in the main study and the sub-study: The Pre BD FEV₁ must be conducted at Visit 2 and at Visit 3. The Pre-BD FEV₁ criteria must be met at either Visit 2 or at Visit 3.
- e For patients in the main study: If the patient did not meet Reversibility criteria at Visit 1, further attempts may be conducted at Visit 2 and at Visit 3. Reversibility testing must be performed using the algorithm as detailed in section 5.1.1.1.
- f For patients in the Body plethysmography sub-study: If the patient did not meet the reversibility criteria (using the algorithm as per section 5.1.1.1) at Visit 1, a further attempt may be conducted at Visit 2 only.

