8.2 Sample size estimate

The study is powered for the primary objective of the study to determine the effect of benralizumab on the time course of change (onset and maintenance of effect) of pre-BD FEV₁. The first post baseline timepoint where the p-value for the mean difference between benralizumab and placebo is less than or equal to 0.05 will be used to determine time to onset of effect. The average over the mean differences between benralizumab and placebo based on the change from baseline (Visit 4) to Days 28 (Visit 8), 56 (Visit 9) and 84 (Visit 10) in pre-BD FEV₁ will be used to determine if the study is positive as well as maintenance of effect.

The benralizumab Phase 2b study MI-CP220 ([Castro et al 2014](#)) as well as results from the benralizumab Phase 3 asthma exacerbation studies were used as a basis for the sample sizing. From these studies, it is expected that around 115 patients per treatment arm (230 in total) will provide approximately 90% power for the primary endpoint pre-BD FEV₁ with type I error controlled at a two-sided alpha level of 0.05 if the true average over the mean treatment differences (benralizumab – placebo) across Days 28 (Visit 8), 56 (Visit 9) and 84 (Visit 10) is 138 mL. The sample size will also be sufficient to have approximately 80% power for an average over the mean treatment difference of 120 mL. The assumed variability has a within group standard deviation of 375 mL and within subject correlation of 0.6. If the within

subject variability is reduced to 350 mL the sample size would be sufficient to have 80% power for an average of 110 mL. In addition, it is expected that around 115 patients per treatment arm will have 80% power to detect a true treatment difference (benralizumab – placebo) of 130 mL assuming a within-group standard deviation of 350 ml or a true treatment difference of 140 mL assuming a standard deviation of 375 mL. Based on these assumptions, the minimum difference that would be statistically significant at the 0.05 level range from approximately 85 to 100 mL. The sample size was estimated using nQuery+nTerim version 3.0 using methodology in (Liu et al 2005)

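### Adding the mean of the run-in (Visits 2 and 3) pre-BD FEV1 as a second covariate in the primary model would gain precision at almost no cost; the plan is not in error without it

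*SAP*

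**What the plan says.** **Primary model.** SAP 4.2.5.1 states: "Treatment group will be fitted as the explanatory variable, region, visit and" the treatment-by-visit interaction as fixed effects, with baseline pre-BD FEV1 as covariate. Protocol 8.5.1 and the synopsis give the same model.

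**Baseline.** SAP 2.2.3 sets the Day 0 value to the average of the two same-day readings (60 and 30 minutes before dosing) when both are of acceptable quality. An earlier reading becomes the baseline only when Visit 4 has no acceptable one.

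**Run-in FEV1.** Protocol section 4, Table 2 footnote d, says that for main-study and sub-study patients the test "must be conducted at Visit 2 and at Visit 3". Section 4.1.3 agrees. Protocol 3.3.2 excludes a patient whose Visit 4 value differs by 20% or more "from the mean pre BD FEV1 calculated from the pre BD FEV1 recorded at Visit 2 and Visit 3".

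**Two qualifications.** Footnote b to protocol Figure 2 (the sub-study flow chart) presents Visit 3 as a second attempt after a failed Visit 2. SAP 8.3, item A.13, foresees missing data for the stability check.

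**The concern.** The outcome is change from Visit 4. If Visit 4 was an unusually good or bad day for a patient, that deviation enters every post-baseline change with the opposite sign. Averaging two readings taken half an hour apart reduces within-session error but leaves day-to-day error in place. Adjusting for Visit 4 FEV1 removes only a small part of it, because most of the Visit 4 variance between patients is their true level. The mean of Visits 2 and 3 estimates that level before randomization, so together with Visit 4 it shows how far Visit 4 was off. What is at stake is the width of the confidence interval for the contrast that decides whether the study is positive, and for the single-visit comparisons from which onset is read. Validity is not at stake.

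**Working it through.** **1. Reproduce the plan's power.** Inputs from protocol 8.2: SD 375 mL, correlation 0.6, 115 per arm, "type I error controlled at a two-sided alpha level of 0.05", and "approximately 90% power for the primary endpoint" when the true average difference "across Days 28 (Visit 8), 56 (Visit 9) and 84 (Visit 10) is 138 mL".

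- Variance of one change: 375² = 140,625. Covariance between visits: 0.6 × 140,625 = 84,375. Visit-specific remainder: 56,250.
- Variance of the three-visit average: 84,375 + 56,250/3 = 103,125, so SD 321.1 mL.
- SE of the treatment difference: 321.1 × √(2/115) = 42.35 mL.
- Power at 138 mL: Φ(138/42.35 − 1.960) = Φ(1.299) = 90.3%. At 120 mL: Φ(0.874) = 80.9%.

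Both stated figures reproduce.

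**2. Assumptions.** The documents do not give the following:

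- between-patient SD τ = 600 mL and mean FEV1 1.8 L;
- visit noise SD σ, independent across visits, of 100, 150, 200 or 237 mL.

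Visit 4 noise is shared by all changes, so response variance + σ² = 84,375. At each post-baseline visit, σ² + any further visit-specific variance = 56,250. Below 237 mL some further variance must be added to keep SD 375 and correlation 0.6. At σ² = 56,250 (σ = 237) none is needed, and the response variance is 28,125 (SD 168 mL).

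**3. Closed form at σ = 237, before the stability rule.**

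- Visit 4 alone removes σ⁴/(τ² + σ²) = 56,250²/416,250 = 7,601. Residual 103,125 − 7,601 = 95,524, SD 309.1 mL.
- Given the run-in mean, the variance of the true level is V = 1/(1/360,000 + 2/56,250) = 26,087. The Visit 4 noise still unexplained is 56,250 × 26,087/(26,087 + 56,250) = 17,822. So 56,250 − 17,822 = 38,428 is removed. Residual 64,697, SD 254.4 mL.
- SE falls by 1 − 254.4/309.1 = 17.7%.

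**4. With the 20% stability rule.** The rule limits how far Visit 4 can lie from the run-in mean, so it already removes part of the problem. Simulated results (run-in and Visit 4 values above 400 mL only):

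| Noise SD (mL) | Residual SD, Visit 4 only | Residual SD, plus run-in mean | Fall in SE | Power at 120 mL |
|---|---|---|---|---|
| 100 | 319 | 310 | 2.9% | 81% → 83% |
| 150 | 314 | 297 | 5.4% | 83% → 87% |
| 200 | 299 | 276 | 7.8% | 86% → 91% |
| 237 | 282 | 254 | 9.8% | 90% → 95% |

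In patients, 1/(1 − 0.029)² = 1.06 and 1/(1 − 0.098)² = 1.23: equivalent to 6-23% more. At 237 mL the rule excludes about a quarter of simulated patients.

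**5. Serially correlated noise.** All noise decays exponentially, response SD is 168 mL, noise SD is 150-237 mL, and no stability rule is applied. The SE of the average falls 7-9% at a 14-day decay constant, 3-4% at 30 days and 1.1-1.5% at 56 days. Slower decay takes it below 1%.

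**6. If 375 mL and 0.6 already describe the Visit 4-adjusted residual.** The protocol does not say. A 10% cut in variance would then move power from 90.3% to 93.0% at 138 mL and from 80.9% to 84.8% at 120 mL. A 20% cut gives 95.4% and 88.6%.

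**The case against.** The strongest reply is that nothing is broken. The model is valid, it adjusts for baseline, and its power claims reproduce. That stands, so a reader who infers that the study is underpowered or the analysis wrong goes further than the documents allow. It also stands that the size of the gain is mostly assumption, and that it nearly disappears if FEV1 drifts slowly over weeks.

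A reader might infer that the early onset tests, Day 3 above all, lose most. The documents do not support a ranking. In the step 4 setting with no response variance yet at Day 3, its SE falls 16.6/13.6/10.6/8.7% for noise SD 100/150/200/237 mL, so at 237 mL it gains less than the average (9.8%). If Day 3 already carries the full late-visit variance it falls 2.1-6.6%, always less than the average. Under the step 5 correlation, Visit 4 and Day 3 share most of their noise, and Day 3 gains under 2% at a 14-day decay constant even with no response variance.

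Two further inferences also fail. The run-in values cannot be assumed present in every patient, given Figure 2 footnote b and SAP 8.3. Nor are they wholly unused, since they serve eligibility and the fallback baseline.

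**Conclusion.** The primary model leaves out a protocol-required, pre-randomization measurement that would be expected to sharpen its main contrast. No structure examined showed a loss. Under independent visit noise and the assumptions in step 2, with the stability rule applied, the SE of the Day 28/56/84 average falls about 3-10%, and power at 120 mL moves from 81-90% to 83-95%. Under noise correlated over weeks the gain may be about 1% or less. The single-visit onset tests also gain, by an amount that depends on the assumptions. This is an efficiency recommendation worth taking because it costs so little. It does not correct an error.

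**What to change.** Before unblinding, add to SAP 4.2.5.1 the mean of the acceptable-quality Visit 2 and Visit 3 pre-BD FEV1 as a second continuous covariate, keeping Visit 4 as the baseline for change. If one run-in value is missing, use the other; if both are missing, use the Visit 4 value. Record the change in SAP section 6, because protocol 8.5.1 fixes the same model. The multiple-imputation analyses in SAP Appendix 8.1 refer back to 4.2.5.1 and so take up the new model. Figure 2 footnote b should be reconciled with Table 2 footnote d and section 4.1.3 of the protocol.

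The cost is one degree of freedom, a short addition to the SAP and a documented departure from the protocol model. No new data or patient burden is involved. The same adjustment for secondary and sub-study endpoints is optional and has not been quantified.
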